#### Confidentiality Statement

Data and information contained in this document are considered to constitute trade secrets and confidential commercial information, and the legal protections provided to such trade secrets and confidential information are hereby claimed under the provisions of applicable law. No part of this document may be publicly disclosed without the written consent of Philip Morris Products S.A.

**Table 1      Relative Exposure/participants groups, measures and sample sizes, according to event type (Non-exposure vs Exposure)**

Variable	Non-Exposure Event	Exposure Event
Participants (group sizes can vary by ± 5%)		
Sample Size required for Non-Exposure and Passive Exposure Group	N = 169	N = 169
• Group 1: Non-Smokers	50%	50%
• Group 2: Cigarette Smokers	25% 	25% 
• Group 3a: IQOS Users (not using IQOS)	25% 	25% 
Total	100% participants in Non-Exposure Events	100% participant passively exposed in Exposure Events
• Group 3b: IQOS Users (using IQOS)	n/a	20% of the total number of available seats in the event location 
Measures		
• Urine (void)	Before Start of the Event, as of ≥2h after start of the Event until the end of the Event (last void analyzed only).	Before Start of the Event, as of ≥2h after start of the Exposure until the end of the Event (last void analyzed only).
• Indoor Air Quality measures	For up to 3h prior to start of the Event; for 3h after the last participant has entered the Event for 1h.	For up to 3h prior to start of the Exposure; for 3h after the last participant has entered and has been exposed for 1h.

 Participants refrain from using any tobacco or nicotine products, including IQOS and/or cigarettes.

 Participants create the exposure to environmental tobacco aerosol through IQOS use.

#### 4.1.1 Step 1: Identification of Participants and Informed Consent: Screening and Enrollment

This step involves the identification of participants, and obtaining informed consent prior to the study (Non-Exposure or Exposure Events). Current adult IQOS Users and Cigarette Smokers will be identified and invited to participate through PMI's product database. A vendor will identify and recruit Non-Smokers from a panel of existing participants used for other research and survey purposes. Additionally, public advertisements might be used.

Potential candidates for participation in the study will be sent a link to a study website to provide information on study details and to complete a Computer-Assisted Self-Interview (CASI) system to assess eligibility and obtain informed consent. After completion of informed consent, the web system proceeds to a "screening domain" of the CASI which is the set of questions and questionnaires to evaluate the participants' eligibility for participation (i.e., inclusion and exclusion criteria, eligible participants).

At the end of the "screening domain" eligible participants will be directed to the "enrollment domain" to confirm their participation in the study. Eligible participants will be presented with the available dates for the Non-Exposure and Exposure Events and asked to confirm his / her preferred dates for participation in maximum one Non-Exposure Event and maximum one Exposure Event. Once a participant confirms participation in the study, they are considered enrolled in the study.

No data will be recorded in the Study Database for the potential participants that do not consent to participate in the study. After consenting for participation in the study, participants can withdraw from the study at any time.. The contact details of the participants, including personal information and personal identifiers will be kept separate from the study data. Subjects will only be compensated for the Non-Exposure or Exposure events they participated in.

#### 4.1.2 Step 2: Non-Exposure Events

The Non-Exposure Events are planned dinner events of 4-hour duration for the individual participant in a restaurant setting with a sufficient number of events ensuring a minimum 169 participants with the following smoking phenotypes: 50% ( $\pm 5\%$ ) of participants are Non-Smokers, 25% ( $\pm 5\%$ ) of participants are IQOS Users (not using IQOS), 25% ( $\pm 5\%$ ) of participants are Cigarette Smokers (not smoking) who are invited to attend a dinner party and enrolled into the study at no cost to them (see [Table 1](#)). The Non-Exposure Events are both nicotine- and tobacco-free (i.e., no nicotine or tobacco products are allowed to be used), and participants must agree to this study requirement. This step allows for non-exposure measurements to be obtained in order to estimate levels of primary endpoints in the absence of IQOS exposure.

---

#### Confidentiality Statement

---

Data and information contained in this document are considered to constitute trade secrets and confidential commercial information, and the legal protections provided to such trade secrets and confidential information are hereby claimed under the provisions of applicable law. No part of this document may be publicly disclosed without the written consent of Philip Morris Products S.A.

---

---

Related to PMI\_RD\_WKI\_000759

IAQ measurements will be sampled for up to 3h prior to the start of the Event and for 3h after the last participant has entered the Event for 1h. Urine specimens per person will be collected for analysis as follows:

The first urine sample will be collected prior to the start of the Event. For the second urine sample, collection will start with the first void after 2 hours of participation in the event to allow sufficient exposure to the event environment to have occurred and therefore detection of BoExp in the urine characterizing the background exposure. From the 2h time point onwards every subsequent void will be collected and the previous urine sample discarded with the last void collected ideally at the end of the 4h exposure period. Only the first and the last urine sample taken (ideally after 4h of participation in the Event) will be analyzed. The time of urine collection will be recorded to ensure that only urine samples taken after 2 hours of participation in the Non-Exposure Event are analyzed.

Urine specimens will also be used to confirm self-reported non-smoking status of the invited participants. Participants who misstate their non-smoking status will not be included in the final analysis.

A fixed menu of food and non-alcoholic and alcoholic beverages typically served in Japanese restaurants will ensure homogeneity of types of potential confounders of both IAQ endpoints and BoExp in the unexposed participant group. The overall amount of food consumed per food type and beverages consumed by type will be recorded.

#### 4.1.3 Step 3: Exposure Events

This step comprises the Exposure Events which will occur in the same restaurant setting as the Non-Exposure Events in order to control for restaurant-related exposures that could confound study results. The first of the Exposure Events will occur within 4 weeks of the Non-Exposure Events and will replicate both the meal, beverages and restaurant dynamics (i.e. same location, air ventilation and table setting) of the Non-Exposure Event.

Exposure Event participants may or may not have attended a Non-Exposure Event, as this is not a study requirement. Participants attend the dinner event at no cost to themselves. These participants represent the same product use phenotypes as in the Non-Exposure Events, except that IQOS Users will be assigned for the Exposure Events to either a) IQOS Users who will use IQOS during the dinner event, or b) IQOS Users who agree not to use IQOS (or any nicotine or tobacco product) during the dinner event (see [Table 1](#)).

The Exposure Events will include a minimum of 169 passively exposure participants with the following product use phenotypes: 50% ( $\pm 5\%$ ) Non-Smokers, 25% ( $\pm 5\%$ ) IQOS Users who refrain from using any nicotine or tobacco product, and 25% ( $\pm 5\%$ ) Cigarette Smokers who refrain from using any nicotine or tobacco products.

---

#### Confidentiality Statement

Data and information contained in this document are considered to constitute trade secrets and confidential commercial information, and the legal protections provided to such trade secrets and confidential information are hereby claimed under the provisions of applicable law. No part of this document may be publicly disclosed without the written consent of Philip Morris Products S.A

---

---

Related to PMI\_RD\_WKI\_000759

In addition, a total of  $20\% \pm 5\%$  of the available seats at the Event location of actively exposed IQOS Users (who use IQOS during the event) will participate in each of the Exposure Events.

Participants actively using IQOS will enter the event location first and start using IQOS *ad libitum* for 1h prior to the other participants (passive Exposure Group) entering the event location.

IAQ measurements will be sampled for up to 3h prior to the start of the Event and for 3h after the last participant was exposed for 1h. Urine specimens per person will be collected for analysis as follows:

The first urine sample will be collected prior to the start of the event. For the second urine sample, collection will only start with the first void after 2 hours of IQOS exposure to allow sufficient exposure to have occurred and therefore detection of BoExp in the urine. From the 2h time point onwards every subsequent void will be collected and the previous urine sample discarded with the last void collected ideally at the end of the 4h exposure period. Only the first and the last urine sample taken (ideally after 4h of exposure) will be analyzed. The time of urine collection will be recorded to ensure that only urine samples taken after 2 hours exposure to IQOS are analyzed.

A fixed menu of food and non-alcoholic and alcoholic beverages typically served in Japanese restaurants will ensure homogeneity of types of potential confounders of both IAQ endpoints and BoExp in the unexposed and passively-exposed participant groups. The overall amount of food consumed per food type and beverages consumed by type will be recorded.

## 4.2 Rationale for Study Design

IQOS is currently used by over 2 million users in Japan. Various restaurants and bars exist where IQOS use is allowed but not CC smoking. This observational study will determine the impact of IQOS use on IAQ and the impact of exposure to environmental tobacco aerosol through measurement of BoExp in urine representative of ETS in a restaurant setting where IQOS use, but not smoking, is allowed.

## 4.3 Appropriateness of Measurements

Nicotine is one of the markers for ETS, however ETS covers several other markers. In this study, ISO Norms related to ETS (15593:2001, 18145:2003 and 11454:1997) are out of scope for indoor air collection as combustion does not occur in THS. Indoor Air Quality Markers selected for assessment in this study are based on:

---

### Confidentiality Statement

---

Data and information contained in this document are considered to constitute trade secrets and confidential commercial information, and the legal protections provided to such trade secrets and confidential information are hereby claimed under the provisions of applicable law. No part of this document may be publicly disclosed without the written consent of Philip Morris Products S.A

---

---

Related to PMI\_RD\_WKI\_000759

1. ISO measurement standards for ETS (ISO Norm 18144:2003)
2. Their relevance for air quality
3. Their relative abundance in THS2.2 aerosol (i.e. the most abundant)
4. Gas-phase tobacco non-specific markers

The BoExp endpoints to assess passive exposure in humans are accepted biomarkers of exposure to ETS, and were furthermore selected based on the following criteria:

1. Availability of a validated analytical method
2. Measure is known to be directly or indirectly affected by the use of tobacco product
3. Timeframe of metabolic decay in the perspective of the study duration
4. Robustness of the method (rapid, simple, accurate)
5. Limited exposure through other sources than tobacco

#### **4.4 Study Duration**

The maximum duration of participants in the Passive Exposure Group will be approximately 4h (not exceeding 5h). The maximum duration of active IQOS use by participants in the Active Exposure Group will be up to 8h ( $\pm 15$  min). Each participant can participate in maximum one Non-Exposure Event and maximum one Exposure Event.

The overall duration of the study is currently planned for 6 weeks, but might be extended based on the number of events needed to secure the necessary number of participants..

End of Study for a participant is defined as the end of the Non-Exposure Event or the last Exposure Event he/she participated in. The overall End of the Study is defined as the end of the last Exposure Event.

### **5 STUDY POPULATION**

A sufficient number of female or male Japanese adult IQOS Users, CC smokers, or Non-Smokers to achieve 169 participants in each of the Non-Exposed and Passive Exposure Groups, who meet the Inclusion criteria below, will be enrolled in the study. In addition a sufficient number of IQOS Users, actively using the product during Exposure Events, will be enrolled to ensure that  $20\% \pm 5\%$  of the available seats of the event location are occupied by

---

 ISO Norms related to ETS (15593:2001, 18145:2003 and 11454:1997) are out of scope for indoor air collection as combustion does not occur in THS.

---

#### **Confidentiality Statement**

Data and information contained in this document are considered to constitute trade secrets and confidential commercial information, and the legal protections provided to such trade secrets and confidential information are hereby claimed under the provisions of applicable law. No part of this document may be publicly disclosed without the written consent of Philip Morris Products S.A

---

---

Related to PMI\_RD\_WKI\_000759

IQOS Users actively using IQOS during the Exposure Event. Distribution of adult IQOS Users, CC smokers or Non-Smokers to these groups are outlined in [Table 1](#).

## 5.1 Selection of Study Population

### 5.1.1 Inclusion Criteria

Participants who meet the following primary inclusion criteria will be enrolled:

- Participant is able to understand the information provided in the Subject Information Sheet (SIS) and informed consent form (ICF) (confirmed by signing the ICF) and has signed the ICF.
- Adults legally authorized to buy tobacco products in Japan (20 years of age).
- Participant is Japanese as self-reported.
- Willing to participate in the study, comply to study procedures and has access to the Internet.
- Participant is an active IQOS User, CC smoker or Non-Smoker as self-reported and as defined in [Table 2](#).

---

**Table 2      Definition of an IQOS User, Cigarette User or Non-Smoker**

Category label	General description
IQOS User (IQOS)	
 
Used at least 100 HeatSticks
 
Uses IQOS daily > 1/day
 
Smokes a cigarette less than daily
 
Smokes less than 30 cigarettes/month
 
IQOS is > 95% of tobacco/nicotine product (all product use) – excluding other products (e-cig/Ploom/etc.)
 

Cigarette Smoker (CC)	
 
Used at least 100 cigarettes
 
Smokes cigarettes daily > 1/day
 
Uses IQOS less than daily
 
Uses less than 30 HeatSticks/month
 
Cigarette is > 95% of tobacco/nicotine product (all product use)
 

Non-Smoker (NS)	
 
Abstinent for at least 12 month from the use of any nicotine and/or tobacco-containing product based on self-reporting.
 
Must not be exposed to tobacco or nicotine-containing products use in any other substantial way (family, partner, workplace, etc.).
 

Note: Details of the product use categories will be reported in the SAP.

### 5.1.2 Exclusion Criteria

Participants who meet any of the following Exclusion Criteria may not be enrolled in the study:

- Participant with a medical history of severe cardiovascular or respiratory diseases (e.g., stroke, acute cardiovascular event, pulmonary thrombosis) in the last 12 months as self-reported.
- Participant with currently active cancer or history of cancer within the last 5 years as self-reported.
- Female participant who is pregnant or breast-feeding as self-reported.
- Participant is a current or former employee of the tobacco industry or their first-degree relatives (parent and child).

#### Confidentiality Statement

Data and information contained in this document are considered to constitute trade secrets and confidential commercial information, and the legal protections provided to such trade secrets and confidential information are hereby claimed under the provisions of applicable law. No part of this document may be publicly disclosed without the written consent of Philip Morris Products S.A

---

Related to PMI\_RD\_WKI\_000759

- Participant is an employee of PMI, [REDACTED] vendors, restaurant/event location employee or their first-degree relatives (parent and child).

Specific to participants who are Non-Smokers:

- Participant lives in a household with users of tobacco or nicotine-containing products, or is exposed to the use of tobacco or nicotine-containing products at the workplace.

## 5.2 Discontinuation of Subjects from the Study

Discontinued participants will include both, participants who withdraw from the study (participants' decision) and participants who are discontinued from the study by the decision of the Principal Investigator. Participants can only be discontinued from the study after enrollment. Participants will be informed that they are free to withdraw from the study at any time. Participants should be questioned for the reason of withdrawal from the study, although they are not obliged to disclose it.

If the patient withdraws from the study during an Event, he/she will be asked whether he/she would agree to still check out procedures ([section 9.3](#)), but with no obligation.

### Discontinuation from the study

Participants must be discontinued from the study for any of the following reasons:

1. Withdrawal of informed consent.
2. The Sponsor terminates the study. If the Sponsor or the Principal Investigator decides to prematurely terminate the study, the participants will be promptly informed. The Sponsor should report the fact and the reason in writing to the IEC/IRB.
3. Participant becomes an employee of any other parties involved in the study.
4. Use of any tobacco or nicotine-containing product (if not allowed).

Participant may be discontinued from the study for the following reasons:

1. Non-compliance to the study procedures based on the judgment of the Principal Investigator.
2. The number of participants has exceeded the number of necessary participants in the Non-Exposure or Exposure Groups.

---

### 5.3 Lost to Follow-up

If a participant has been enrolled in the study via the Study Website but does not show up at the scheduled events, no attempt to follow-up with the participant will be made and the participant will be marked as “no show”.

### 5.4 Violation of Selection Criteria

Any participant who is in violation of selection criteria as checked at Screening or prior to each Event shall be discontinued from the study.

## 6 INVESTIGATIONAL PRODUCTS

### 6.1 Description of Investigational Products

The product tested in this study is the Tobacco Heating System (THS) with *Marlboro Heatsticks*, marketed in Japan under the brand name IQOS and generally referred to as IQOS in this protocol. All versions of IQOS and *Marlboro Heatsticks* available for sale in Japan at the time or prior to the Study start or becoming available during the course of the Study are allowed to be used in the context of this study. IQOS is composed of the following components: a tobacco *HeatStick*, a Holder and a Charger ([Table 3](#)), as well as a cleaning tool, a power supply, and a USB cable.

---

**Table 3 Test Product (IQOS)**

Component	Description
HeatStick	
The HeatStick is designed to function with the Holder. The HeatStick is made up of: tobacco plug, hollow acetate tube, polymer-film filter, mouth piece filter, outer and mouth-end papers.
 
All materials have been evaluated with regards to their toxicological potential and have been approved for use.
 
The tobacco plug is made from tobacco, glycerin, water, guar gum, cellulose, propylene glycol, natural and artificial flavorings.
 
The average amount of nicotine in the tobacco plug is 4.3-5.4 mg/stick per HeatStick.

Holder	
The Holder is a slim electrical heating unit that heats the HeatStick in a controlled manner by using a heater blade.
 
The Holder stores enough energy for a single experience, delivering consecutive puffs over a period of about 6 minutes or 14 puffs (whichever comes first). A Light Emitting Diode indicates the end of the experience.
 
Once this cycle is complete, the Holder must be recharged before a new HeatStick can be used.

Charger	
The power supply for the Holder is the Charger.
 
The Charger holds enough energy for approximately 20 uses of the Holder and can be recharged from household power.
 
The Charger stores the Holder when not in use, and provides a secure environment for the cleaning process of the heater blade.

The overall objective of the product design is to provide an acceptable experience in which the HPHCs levels in the aerosol are substantially reduced in comparison with the smoke of a cigarette [20, 34]. A summary of description of the product, pre-clinical and clinical data available on IQOS is provided in the SPI [35].

## 6.2 Use of Investigational Product(s)

Participants in the Active Exposure Group (IQOS use) will be asked to bring their own IQOS device and *HeatSticks* for their own use during the entire study period as *HeatSticks* will not be provided by the Sponsor. Participants in the Active Exposure Group will use IQOS *ad libitum* with no *Heatsticks* variant restrictions.

Urine samples collected during the study will also be used to verify self-reported smoking status as well as compliance with protocol restrictions on IQOS and cigarette use during the events.

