#### 6.2.1 From Screening to Event Participation

There are no restrictions on use of IQOS or cigarettes or any other tobacco or nicotine-containing products during screening until participation in any of the events.

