### 6.5.2 Adherence to allocated Exposure

Adherence to allocated Exposure, no use of any tobacco or nicotine-containing product during the Non-Exposure Events and no use of any tobacco or nicotine-containing product during the Exposure Events, with the exception of the Active Exposure Group, will be monitored by the staff at the Event location. Any product use by any participant in the Passive Exposure Group and any product use other than IQOS in the Active Exposure Group will lead to the discontinuation of the participant from the study.

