7.1.3 Step 3: Exposure Events

This step comprises the Exposure Events which will occur in the same restaurant setting as the Non-Exposure Events in order to control for restaurant-related exposures (i.e., location, air ventilation and table setting) that could confound study results. The first of the Exposure Events will occur within 4 weeks of the Non-Exposure Events. The Exposure Events will replicate the meal, beverages and restaurant dynamics of the Non-Exposure Event.

Exposure Event participants may or may not have attended a Non-Exposure Event. Participants attend the dinner Event at no cost to themselves. The participants who attend more than one event will represent the same product use phenotypes for both events, except the IQOS Users will be assigned for the Exposure Events to either a) an IQOS Active User, or b) an IQOS Passive User (see [Table 1](#)).

The Exposure Events will include a minimum of 169 passively exposed participants. During each Exposure Event a total of $20\% \pm 5\%$ of the available seats at the Event location will be allocated to IQOS Active Users (who use IQOS during the event). The remaining seats will consist of passively exposed participants with the following product use phenotypes: 50% ($\pm 5\%$) Non-Smokers, 25% ($\pm 5\%$) IQOS Passive Users who refrain from using any nicotine or tobacco product, and 25% ($\pm 5\%$) Cigarette Smokers who refrain from using any nicotine or tobacco products.

IQOS Active Users will enter the event location first and start using IQOS *ad-libitum* for 1h prior to the other participants (passive Exposure Group) entering the event location.

IAQ measurements will be sampled for up to 3h prior to the start of the Event and for 3h after the last participant was exposed for 1h. Urine specimens per person will be collected for analysis as follows:

The first urine sample will be collected prior to the start of the event. For the second urine sample, collection will only start with the first void after 2 hours of IQOS exposure to allow sufficient exposure to have occurred and therefore detection of BoExp in the urine. From the 2h time point onwards every subsequent void will be collected and the previous urine sample discarded with the last void collected ideally at the end of the 4h exposure period. Only the first and the last urine sample taken will be analyzed.

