11.2 Compliant Exposure Set

The Compliant Exposure Set will consist of all enrolled participants who signed the ICF and who participated in either a Non-Exposure Event or an Exposure Event, have provided two urine samples (one urine sample prior to the event and one sample after a minimum 2h of participation in the Event) and are compliant with the Event Exposure Groups (Non-Exposure or Passive Exposure).

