12.6 Planned Statistical Analyses

12.6.1 Primary Analysis

12.6.1.1 Statistical Analysis of Primary Endpoints

For each urinary BoExp in the primary analysis NEQ, Total NNAL, Total NNN, the change between pre-event and end of study levels adjusted for creatinine will be modeled using a linear model in the Compliant Exposure Set.

The SAS procedure PROC MIXED will be used with the restricted maximum likelihood method for estimation of the parameters. The mixed model will have the change from baseline as dependent variable and the following covariates will be included in the model: Baseline, Sex, Event Type (Exposure or Non-Exposure), Duration of Exposure, Product Use Status, Product Use Status by Event Type interaction for all BoExp. In addition, an air quality covariate related to each BoExp is included in the model depending on the endpoint and is described in Appendix 15.2. This table also specifies the various IAQ covariates that are assessed using a step-wise regression approach for each BoExp. The algorithm is described below,

1. Fit a full model with all covariates

2. Drop one IAQ covariate and re-fit the model.
3. Perform a likelihood ratio test and drop the IAQ covariate with the largest p-value for the likelihood ratio statistic if it is more than 0.05.
4. Repeat steps 2 and 3 until no more IAQ covariates can be dropped.
5. Refit the final model with the IAQ covariates remaining in the model and estimate exposures for each product use group.

Appropriate contrasts will be constructed to determine the effect of passive exposure to IQOS aerosol during the Exposure Event on the mean change in levels of urinary BoExp together with the 95% CIs for non-smokers during an Exposure Event. Other contrasts can be constructed to determine the change in urinary BoExp for participants with other smoking status (Cigarette Smoker and IQOS Passive Users) after passive exposure to IQOS usage.

An example of SAS code for the final model is provided below,

```
Proc mixed data=_data_ method=reml;
Class event_type sex product_use;
Model endpoint = baseline sex event_type product_use event_type*product_use
duration <IAQ covariates> / ddfm=kr;
estimate 'Cigarette Smoker' intercept 1 baseline xx sex .5 .5 product_use 1 0 0
event type 1 event_type*product_use 1 0 0 0 0 duration xx IAQ1 xx ... IAQn xx /
alpha=0.05 cl;
Run;
```

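### Using study urine to verify product abstinence during the events would, if it led to exclusions, select on the co-primary outcome; event compliance should be decided from staff records before urine results are seen

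*Protocol*

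**What the plan says.** **Role of urine.** Protocol 6.2 gives study urine two checking roles. One is declared smoking status. The other is use during the events: "as well as compliance with protocol restrictions on IQOS and cigarette use during the events".

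**Consequence of prohibited use.** Protocol 5.2 lists use of a product where it is not allowed among the reasons for mandatory discontinuation, and 6.5.2 repeats this for the Passive Exposure Group. Protocol 12.3.1 and SAP 11.2 make compliance a condition of the main analysis set. In the SAP's words, members must have given two urine samples "and are compliant with the Event Exposure Groups (Non-Exposure or Passive Exposure").

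**Other check on use.** Protocol 6.5.2 says that adherence "will be monitored by the staff at the Event location". Protocol 6.6.3 has staff record unallocated use, with a check by the Principal Investigator or a designee. Tables 7 and 8 add a confirmation at the end of each event.

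**Outcome.** SAP 12.6.1.1 names the endpoints: "For each urinary BoExp in the primary analysis NEQ, Total NNAL, Total NNN". It then states: "The mixed model will have the change from baseline as dependent variable". On samples, SAP 7.1.3 says: "Only the first and the last urine sample taken will be analyzed".

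**Use before the event.** Protocol 6.2.1 says: "There are no restrictions on use of IQOS or cigarettes or any other tobacco or nicotine-containing products during screening until participation" in any event. Protocol 6.2.4 and 6.6.1 are to the same effect.

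**The concern.** The biomarkers that would reveal covert use during an event are the ones the study measures to detect passive exposure. In a Non-Smoker, a rise in nicotine equivalents between the two voids is the signal sought and is also what undeclared use would produce. In Cigarette Smokers and IQOS Passive Users, unrestricted use before arrival adds a further source that the last void cannot be assumed to separate from use during the event.

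If a high last-void result is read as non-compliance, the participant leaves the main set because of the outcome value. That lowers the estimated change. Protocol 2.2 states that the study aims to show Non-Smokers do not have higher levels after exposure, so the bias would favour the conclusion sought. There is no blinding, and SAP 13.3 places a data review meeting before database lock, so an undefined rule would be settled by judgement.

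**Working it through.** **Step 1. Which sample can inform the check.** Two voids per event are analysed. The pre-event void is taken before entry and cannot show use during the event. Voids from 2 h onward are collected, but each earlier one is discarded (Protocol 4.1.2, 4.1.3). Only the last void remains. The dependent variable is the change from the pre-event void to that last void, so the check and the outcome share the same measurement.

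**Step 2. What rule the documents give.** For smoking status, SAP 7.1.2 gives one: Total NNAL over 75.9 pg/mL, Non-Smokers only. For event compliance by urine, neither document gives an analyte, sample, cut-off or decision-maker.

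**Step 3. The plan's own figure.** The only design figure is 169 participants per event type. It cannot be reproduced, because Protocol 12.2 and SAP 9 give no effect size, SD or power. The point does not depend on it. Half of 169 gives 84.5, so about 85 Non-Smokers per event type.

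**Step 4. Illustration of the bias.** All values here are assumed. In SD units, let the change be N(d, 1) at Exposure Events and N(0, 1) at Non-Exposure Events. Anyone at either event type whose change exceeds k is removed. The mean of those kept is

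m(μ, k) = μ − φ(k − μ)/Φ(k − μ),

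and the difference kept is m(d, k) − m(0, k).

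Worked case, d = 0.5 and k = 1.645:
- Exposure: 0.5 − φ(1.145)/Φ(1.145) = 0.263
- Non-Exposure: 0 − φ(1.645)/Φ(1.645) = −0.109
- Difference kept: 0.263 + 0.109 = 0.372, or 74% of 0.5
- Non-Smokers removed: 0.126 × 84.5 = 10.7 exposed, against 0.050 × 84.5 = 4.2 unexposed

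| Cut-off k (SD) | d = 0.25 | d = 0.5 | d = 1.0 |
|---|---|---|---|
| 1.645 | 78% | 74% | 67% |
| 2 | 86% | 83% | 77% |
| 3 | 98% | 97% | 95% |

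Entries are the share of the true between-event difference that remains. Every entry is below 100%.

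**Step 5. The Exposure Event mean alone.** SAP 14.1 says the planned model estimated levels for each event type without comparing them; the comparison was added post hoc. Trimming the Non-Exposure Events does not offset the bias in the Exposure Event mean. With d = 0.5, the mean kept is 0.263 at k = 1.645 and 0.482 at k = 3.

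**Step 6. Compliance decided without the last void.** If exclusion does not depend on the last-void value, this truncation bias is zero in the illustration.

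**The case against.** The strongest reply is that no urine-based event exclusion exists on paper. Protocol 6.2 speaks of verifying and attaches no consequence to the result. SAP 11.2 mentions no urine level. The check set out in detail is staff monitoring, recording and end-of-event confirmation. The SAP's only urine exclusion concerns non-smoking status, which is a separate matter. This stands: a reader might infer that the plan, applied as written, strips out the largest rises, and the documents do not support that. What remains is that Protocol 6.2 states urine will serve this purpose, prohibited use leads to discontinuation, and the main set requires compliance. SAP 11.2 does not rule urine out.

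A second reply is that urine may separate the two in Non-Smokers. A reader might infer that it can never tell covert use from passive exposure. That is too absolute: the documents do not show that the two overlap in size, and a cut-off well above passive rises costs little (2-5% at 3 SD). Nor does carry-over from earlier use arise for Non-Smokers abstinent for 12 months. This also stands, but no such cut-off is specified.

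Third, the exclusions would not be hidden. SAP 15.4 plans a table of analysis sets with reasons for exclusion (15.2.1.3.2) and a matching listing (15.3.1.4). That gives visibility, but it does not remove a bias from the main estimate.

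Finally, dropping the check gives up an objective guard against unobserved use, which could inflate Non-Smoker changes. That is a fair cost, and a sensitivity analysis addresses it.

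**Conclusion.** The point holds as a conditional one. The protocol assigns urine a role in judging event compliance and gives no rule for it. The only analysed sample that could serve is the one that supplies the co-primary outcome. If exclusions follow from it, the analysis selects on the outcome and the estimated effect of passive exposure moves towards no effect.

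The loss is small (about 2-5% of a true between-event difference) for a cut-off well above passive rises, and material (about 22-33%) for a cut-off of 1.645 SD, which lies within them. These figures assume normal changes with equal SD, true differences of 0.25 to 1.0 SD, and one cut-off applied at both event types. They ignore the model's covariates. The documents give neither a cut-off nor an SD, so the figures show direction and scale and do not predict what happened in this study.

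**What to change.** - **SAP 11.2:** define event compliance only from staff observation and recorded product use (Protocol 6.5.2, 6.6.3, Tables 7 and 8), decided and documented before urine results are seen. State that no one leaves the main set for event non-compliance because of a last-void value.
- **Protocol 6.2:** remove the event-compliance clause, or limit it to match.
- **Sensitivity analysis:** treat any urine-based suspicion of use during an event as a labelled sensitivity analysis, stating the analyte and cut-off used. Report numbers by event type and product use group.
- **If exclusions have already been made:** SAP version 3.0 adds analyses after results were reviewed, so a wording change alone may come too late. Report any exclusion that rests on urine, and re-include those participants in a sensitivity analysis.

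The cost is a few sentences in two documents and one extra analysis. The downside is that a few unobserved covert users may stay in the main set.
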